
- 5.2 Procedures for recruiting focus groups - Providers (Aim 1.1). [name] will email her colleagues at Brigham and Women's and DFCI to recruit them for a 60- minute focus group discussion, aimed to occur at a regular weekly/monthly meeting for a particular PCP or medical oncology practice. We will provide beverages and snacks for the meeting. We will visit the practice at BWH or DFCI to conduct the focus groups and any virtual focus groups will take place by phone via webex. [name] will also reach out to her broad network of physicians outside of DFCI to recruit oncologists from around the country for the virtual focus group (which will occur via

PROTOCOL TITLE:

webex/phone). [name] (who is experienced in leading clinician-based focus groups) will lead all clinician focus groups. All discussions will be recorded and professionally transcribed. At the start of the clinician focus groups, verbal consent from each participant will be obtained and providers will be provided a written copy of the verbal consent in person or via email. We do not intend to register providers in Oncpro.

- 5.3 Procedures for recruiting providers and patients for the tool intervention (Aim 1.2)
We will then test the communication tool at DFCI, DFCI at South Shore Hospital , and DFCI at St. Elizabeth's breast medical oncology practices. [name] will recruit 10-12 medical oncology colleagues who each agree to test the communication tool in ≤5 of their older patients over a 4-6-week period.

Before the visit. To identify mammography-eligible patients with low-to-average risk for in-breast recurrences, the dedicated CRC will scan participating clinician schedules daily over a 4-6-week period at DFCI/St. E's/South Shore Hospital for breast cancer patients with stage 0-II breast cancer who have completed any chemotherapy, surgery, and/or radiation ≥12 months prior and who are aged ≥75 and who had breast-conserving surgery. If a patient meets criteria for possible enrollment, the CRC will email the clinician (Appendix H) to confirm that mammography would typically be discussed at this visit and to ask permission to offer the study to the patient.

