will ask the patient to complete the paper ‘post’ surveys in person, by mail, or by email within 7 days of the appointment, concluding the study for that patient. To understand how providers feel about the communication tool, the experience using it, and the comfort with it as a guide for discussions, the clinician will be asked to complete one brief survey per patient enrolled (no provider consent planned but a short introduction to the survey will be provided-see Appendix D), after all of their participating patients have completed their visits. Each patient will be registered to document their participation by DFCI study staff and will receive a \$40 gift card for their participation and clinicians will receive a \$40 gift card after the all surveys for participating patients have been completed. All data will be entered by the CRC into the secure, REDCap.

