5.4 Registration Procedures

The eligibility checklist (Aim 1.2 only) will be filled out and submitted by the DFCI Study Coordinator for registration within 30 days of the patient participant providing verbal consent at the time of the survey. The other qualitative aims will not require study registration. Registered study participants from Aim 1.2 will be entered on study centrally at DFCI by the Study Coordinator after providing verbal consent. All registrations must occur within 30 days of the survey date.

The Study Coordinator will follow DF/HCC policy (REGIST-101) and register eligible participants on the protocol using the Clinical Trials Management System (CTMS) OnCore. Following registration, the Study Coordinator will use the participant study number for identification of all patients.

Participant information, including receipt of verbal consent, will be tracked in a password-protected, secure, on-line, web-based system. We will also secure patient contact information on this portal in addition to a tracking sheets on the number of phone calls made and any contact made with potential participants. Anyone failing screening or declining enrollment will be logged internally (not centrally by ODQ) and confidentially by study staff with the reason for failure or decline.

6.0 **Multi-Site Research**

All patient research will be conducted on site at DFCI, DFCI at South Shore Hospital, and DFCI at St. Elizabeth’s, or by phone. Provider focus groups will take place at DFCI, Brigham and Women’s, or virtually/by phone. Although [name] is a collaborator on this study, no research will take place at BIDMC.

7.0 **Study Timelines**

7.1 Duration of the study:

- The patient and providers are each involved for one time-point.
- We anticipate that all aims will be completed by December 31, 2020.

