- 8.4 Outcomes and Analyses for Aim 1.2. The outcomes of interest are shown in Table 2 below and have been adapted from [name] prior survey study testing a decision aid for screening mammography for older women.⁶⁶ We will focus on a primary outcome of intentions for mammography and will examine how various factors (race, health literacy, numeracy, anxiety, life expectancy) impact intentions. We use the sign rank and exact McNemar’s testing to compare the ‘pre’ vs. ‘post’ results for the continuous score for intention and proportion who indicate ‘yes’, respectively. To account for clustering by clinician, we will utilize random effects models if parametric assumptions hold, or alternatively using bootstrap resampling techniques to compute 95% confidence intervals for the change in intention. We anticipate a low number of missed surveys because of the CRC follow-up planned by phone, mail, or email if necessary. If a patient is missed for her ‘pre’ test survey, we will replace her to ensure enrollment of 45 with ‘pre’ and ‘post’ surveys. We will compare characteristics of those with missing surveys and missing questions to those with complete surveys to assess for any notable differences.

Table 2. Outcomes of Interest for Aim 1.2	
Outcome(s) of Interest	Outcome definitions, planned analyses

PROTOCOL TITLE:

Primary Outcomes: Patients: Frequency of change in intentions for mammography in the next year	15 point validated scale to assess ‘pre’ vs ‘post’ survey responses where scores 1-5 = yes to having mammography, 6-10 = unsure, 11-15 = no for mammography. We will use a continuous outcome of 1-15. ^{66,79}
Patients & Clinicians: Acceptability & Feasibility	Length, clarity; tabulate responses ⁸⁰ ; 75% report the tool is useful
Secondary Outcomes:	
Clinicians: satisfaction, time added/removed	Tabulate responses, prepare descriptive analyses
Patients: preferred decision-making role	‘Pre’ survey: Examine preferences for active, shared, passive decision-making ⁸¹
Patients: Decisional conflict	‘Pre’ vs. ‘Post’ survey: 16 item scale, Calculate total and sub-scale responses. Scores range 1-100, lower scores indicating higher quality decision-making ^{82,83}
Patients: Knowledge about mammography	Number of correct (10) knowledge questions on ‘pre’ vs. ‘post’ surveys. ^{66,84,85}

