****Post-visit Clinician Questionnaire****

Thank you for agreeing to participate in this study. We are going to ask you some questions relating to this particular visit with the patient. All of your answers will be kept confidential, will not be linked to your name for future use, and are for informational purposes only as we try to understand how helpful this tool was in your discussions with patients. Please answer openly and honestly and you can skip any question you prefer not to answer

Study ID _____

Date: _____

Intentions for mammography

1. What did you recommend in terms of mammograms for this patient?

- Continue having mammograms
- Get another mammogram but consider stopping after that
- It is the patient's choice
- To not get a mammogram now but reconsider later
- To stop getting mammograms
- Did not discuss mammograms
- Other: _____

2. Before the visit, what did you think you would recommend?

- Continue having mammograms
- Get another mammogram but consider stopping after that
- It is the patient's choice
- To not get a mammogram now but reconsider later
- To stop getting mammograms
- I did not think I would discuss mammograms
- Other: _____

3. During the visit today, did you discuss any of the following (circle each answer):

- | | | | |
|--|-----|----|----------|
| • Pros of mammograms? | Yes | No | Not sure |
| • Cons of mammograms? | Yes | No | Not sure |
| • The patients individual risk of in-breast, pre-cancer or invasive cancer events? | Yes | No | Not sure |
| • Family history? | Yes | No | Not sure |
| • Life expectancy? | Yes | No | Not sure |

PROTOCOL TITLE:

- Any other relevant discussion points you discussed?
-

3A. If yes to discussing life expectancy, how did this go? Check any that apply:

- Helpful to patient
- Helpful to me
- It was uncomfortable
- It was comfortable
- Made decision-making easier for mammogram
- Made decision-making harder for mammogram
- Neutral effect on decision-making
- Other _____

3B. If no to discussing life expectancy above, why not? Check any that apply

- It didn't come up
- I was uncomfortable talking about it
- Patient did not want to discuss it
- Patient was anxious
- Patient healthy so I didn't think it was important
- I didn't have time
- I didn't think it was important for this discussion

Questions about the Communication Sheet (with regard to its use during this visit with the patient)

4. The length of the communication sheet was

- | | | | | | |

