9. Would you recommend the use of this communication tool?

- | | | | |
|--------------------------|--------------------------|---------------------------|-----------------------------|
|  |  |  |  |
| Definitely
Recommend | Probably
Recommend | Probably not
Recommend | Definitely not
Recommend |

It would be helpful to learn how you prefer to use health educational materials such as the one you used today.

10. What is your preferred format for health education materials:

- A pamphlet like the one you used for this study
- The computer/internet
- No preference
- Other _____

11. How did using this tool affect the length of the visit with your patient today?

- Made visit a lot longer
- Made visit a little longer
- No effect on visit time
- Made visit a little shorter
- Made visit a lot shorter
- Not sure
- Other
- I didn't use it

12. Please let us know about any other thoughts you have about using the tool in practice. Please be as honest as possible.

Thank you so much for your help. You will receive a one-time \$40 at the end of this study for participating in these surveys.

PROTOCOL TITLE:

CITATIONS

****All questionnaires are adapted and revised from validated surveys used in the following publications :*

Decision Aid evaluation for screening by Schonberg M.A. et al JAMA Intern Med 2014; 174(416-424),

https://decisionaid.ohri.ca/docs/develop/User_Manuals/UM_ChoicePredisposition_Decision.pdf,

https://decisionaid.ohri.ca/docs/develop/Tools/DCS_English.pdf,

https://decisionaid.ohri.ca/docs/develop/Tools/Acceptability_osteoporosis.pdf)

Gotay CC and Pagano. Assessment of Survivor Concerns: A newly proposed brief questionnaire. Health Qual Life Outcomes 2007; 5: 15.

PROTOCOL TITLE:

**APPENDIX E: VERBAL CONSENT FOR THE PATIENT PHONE INTERVIEWS
AND FOCUS GROUPS**

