Per our medical record review, it seems that *[name] is aged 75 or older, had breast conservation, and is in long-term follow-up care for her breast cancer. She is likely eligible for protocol 19-001.* As you may know, this is survey-based study where patients will be given an information tool to discuss mammography with you that can be used as you like and per your discretion. Patients will be surveyed before and after your visit on their mammography decisions and how the information tool may have helped/not helped them make decisions. Participants will receive \$40 for their time. ***This cohort is purely survey-based and there is no therapeutic component to the study.***

If we do not hear from you within 2 business days, we will assume permission to initiate contact with the patient. We will mail your patient an introduction to the study and then call them a week later to assess their interest. If this patient is interested in participating, we will be responsible for consenting her and for all study procedures. **We will survey you at the end of the patient encounter via email and at the end of the study, you will receive a \$40 amazon gift card in appreciation of your time.**

Thank you for your assistance and support of this study. Please feel free to contact us if you have any questions.

Sincerely,

[name], MPH

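### Section 5.3 and Appendix H give different timings for the clinician survey, and following 5.3 means visit-specific answers are recalled weeks late

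*Protocol*

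**What the plan says.** The protocol describes the timing of the Aim 1.2 clinician survey in several places.

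- **Section 5.3, Visit Day.** One short survey for each enrolled patient, requested "after all of their participating patients have completed their visits". No completion deadline is given, although the same section gives patients 7 days for their post survey. Each clinician agrees to "test the communication tool in ≤5 of their older patients over a 4-6-week period".
- **Section 7.1.** "The patient and providers are each involved for one time-point".
- **Appendix H (email to the clinician about a named patient).** "We will survey you at the end of the patient encounter via email". The gift card is placed separately, at the end of the study.
- **Appendix D, Post-visit Clinician Questionnaire.** Item 3: "During the visit today, did you discuss any of the following". Item 11: "How did using this tool affect the length of the visit with your patient today". Item 2 asks after the event about the plan before it: "Before the visit, what did you think you would recommend".

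On use of the data, section 8.4 (Table 2) lists clinician "satisfaction, time added/removed" as a secondary outcome. The SAP says that clinician answers to patient-relevant questions were described for each participating patient. It gives as examples the recommendation made and whether pros and cons were discussed. It does not say when the forms were completed.

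**The concern.** Study staff working from 5.3 and clinicians working from Appendix H would expect different schedules, and the form fits only the second. The choice affects the data. The form records facts about one visit: the recommendation, the topics covered, whether life expectancy came up, and whether the tool lengthened or shortened the appointment. Under 5.3 these are collected in a batch, after other study patients have been seen with the same tool. A clinician completing four or five near-identical forms at once may not reliably place each discussion, or each judgement of visit length, with the right patient.

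What is at stake is the patient-level clinician description in the SAP and the time outcome in Table 2. The patient's own intention, knowledge and decisional conflict scores come from her own surveys and are not affected. No effect is claimed on the planned patient–clinician agreement on the 1–15 scale.

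**Working it through.** **Comparing the texts.** The Appendix H email is sent for each potentially eligible patient and names her, so the encounter it mentions is that one visit. It dates the survey and the gift card separately, so it cannot be read as an end-of-study survey. Section 5.3 places the survey after the clinician's last participating patient. For every patient but the last, the two cannot both be followed. Section 7.1 fits 5.3 better than a survey after each visit, but it is loose wording: it also covers patients, who answer twice. It is secondary evidence only.

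**Size of the delay if 5.3 is followed.** The plan gives no figure to reproduce.

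Inputs from the protocol: 45 patients (section 4.1); 10–12 clinicians, at most 5 patients each, over 4–6 weeks (section 5.3).

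Assumptions: patients split as evenly as possible; each clinician's k visits fall independently and uniformly over T weeks; forms are completed on the day of that clinician's last visit.

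Even splits of 45:
- 10 clinicians: five with 5 patients, five with 4
- 11 clinicians: one with 5, ten with 4
- 12 clinicians: nine with 4, three with 3

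Formulas (T in weeks):
- The last visit is expected at Tk/(k+1), the average visit at T/2 and the first at T/(k+1).
- Mean lag = Tk/(k+1) − T/2 = T(k−1)/(2(k+1)).
- First-patient lag = T(k−1)/(k+1).
- P(lag > 1 week) = 1 − 1/T − (1 − T^−k)/k.

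Values by k:

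| k | T | Mean lag (wk) | First-patient lag (wk) | P(lag > 1 wk) |
|---|---|---|---|---|
| 3 | 4 | 1.00 | 2.00 | 0.422 |
| 4 | 4 | 1.20 | 2.40 | 0.501 |
| 5 | 4 | 1.33 | 2.67 | 0.550 |
| 3 | 6 | 1.50 | 3.00 | 0.502 |
| 4 | 6 | 1.80 | 3.60 | 0.584 |
| 5 | 6 | 2.00 | 4.00 | 0.633 |

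Worked case, 10 clinicians and T = 4:
- Mean lag = (25 × 1.333 + 20 × 1.20)/45 = 1.27 weeks.
- First-patient lag = (5 × 2.667 + 5 × 2.40)/10 = 2.53 weeks.
- Forms beyond 7 days = 25 × 0.550 + 20 × 0.501 = 23.8.

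All cases:

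| Clinicians | T | Mean lag (wk) | First-patient lag (wk) | Forms > 7 days, of 45 |
|---|---|---|---|---|
| 10 | 4 | 1.27 | 2.53 | 23.8 |
| 10 | 6 | 1.91 | 3.80 | 27.5 |
| 11 | 4 | 1.22 | 2.42 | 22.8 |
| 11 | 6 | 1.82 | 3.64 | 26.5 |
| 12 | 4 | 1.16 | 2.30 | 21.8 |
| 12 | 6 | 1.74 | 3.45 | 25.5 |

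Simulation agrees with the formulas. The share beyond 7 days is 48.5% (21.83/45) to 61.1% (27.5/45). The longest possible scheduled lag is the whole window, 4–6 weeks. Each clinician's last patient has no scheduled lag: 10/45 = 22% to 12/45 = 27% of forms.

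**Sensitivity.** If a clinician's four visits fell within 2 weeks, the mean lag would be 2 × 3/(2 × 5) = 0.6 weeks, and 1 − 1/2 − (1 − 1/16)/4 = 27% of forms would exceed 7 days. If accrual ran past 6 weeks, or forms came back late, delays would be longer than tabulated.

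**The case against.** Several points can be made for the plan.

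**Batching may suit the purpose.** Section 5.3 says the survey is meant to learn how providers feel about the tool and their comfort with it, and a view formed after several uses is reasonable for that. But one overall survey would then be enough. The protocol asks for one per patient, with items that make sense only for a single visit.

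**A form after every visit could prime the clinician.** Being asked whether pros, cons and life expectancy were covered might change counselling of later study patients, and so touch patient intention, a primary outcome. This stands as a real trade-off. It looks marginal, because 5.3 already gives clinicians a reminder and a copy of the tool before each study visit, and because Appendix H already promises a survey per encounter.

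**Delay is not error.** Seven days is the patients' window, not an established recall limit for clinicians. Clinicians might check their notes for the recommendation or topics discussed, though notes would help less with visit length. No misclassification rate is estimated here. All of this stands and limits the claim.

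**The data appear to be in.** The SAP is written in the past tense, so redesign may come too late. The fix therefore includes what can still be reported.

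**The outputs are descriptive, in a 45-patient pilot, and the email and forms are labelled drafts.** True, and that keeps the weight moderate. It does not remove the contradiction.

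**Conclusion.** The contradiction is certain: 5.3 and Appendix H prescribe different timings, the form matches Appendix H, and nothing in either document reconciles them. The consequence is conditional on 5.3 being the schedule followed. In that case, under an even split and uniform visits, the mean delay is 1.2–1.9 weeks, the first patient of each clinician averages 2.3–3.8 weeks, and roughly half to three fifths of forms fall beyond 7 days. These figures measure delay; the resulting error cannot be sized from the documents. The damage is confined to the visit-specific clinician items and the time outcome. Item 2, the plan before the visit, is retrospective under either schedule. The point should be corrected, but it does not threaten the patient-reported results.

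**What to change.** **If surveys are still to be collected:**
- Change 5.3 to match Appendix H: email the survey at the end of each enrolled patient's visit, for completion the same day where possible and within 7 days at the latest, with one reminder. Keep the gift card at the end of the clinician's participation.
- Amend 7.1 to say that providers respond once per enrolled patient.
- On the form, replace the same-day wording with the dated visit. Define the single date field as the completion date and pair it with a separately recorded visit date.
- Report the visit-to-survey interval, flag forms returned after 7 days, and label item 2 as retrospective.

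**If data are already collected:** state in the SAP and the report which timing was used, give the interval where both dates can be recovered, and label item 2 as retrospective.

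**Cost.** One sentence each in 5.3 and 7.1, a wording change on the form and a REDCap trigger. Clinicians receive up to five short emails instead of one batch. The small priming risk remains and should be acknowledged.

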5.4 Registration Procedures

The eligibility checklist (Aim 1.2 only) will be filled out and submitted by the DFCI Study Coordinator for registration within 30 days of the patient participant providing verbal consent at the time of the survey. The other qualitative aims will not require study registration. Registered study participants from Aim 1.2 will be entered on study centrally at DFCI by the Study Coordinator after providing verbal consent. All registrations must occur within 30 days of the survey date.

The Study Coordinator will follow DF/HCC policy (REGIST-101) and register eligible participants on the protocol using the Clinical Trials Management System (CTMS) OnCore. Following registration, the Study Coordinator will use the participant study number for identification of all patients.

Participant information, including receipt of verbal consent, will be tracked in a password-protected, secure, on-line, web-based system. We will also secure patient contact information on this portal in addition to a tracking sheets on the number of phone calls made and any contact made with potential participants. Anyone failing screening or declining enrollment will be logged internally (not centrally by ODQ) and confidentially by study staff with the reason for failure or decline.

6.0 **Multi-Site Research**

All patient research will be conducted on site at DFCI, DFCI at South Shore Hospital, and DFCI at St. Elizabeth’s, or by phone. Provider focus groups will take place at DFCI, Brigham and Women’s, or virtually/by phone. Although [name] is a collaborator on this study, no research will take place at BIDMC.

7.0 **Study Timelines**

7.1 Duration of the study:

- The patient and providers are each involved for one time-point.
- We anticipate that all aims will be completed by December 31, 2020.

8.0 Study Endpoints, Statistical Plan, and Sample Size Considerations

- 8.1 Aim 1.1 (provider focus groups and patient interviews). For each discussion, the transcribed data will be analyzed according to standard comprehensive qualitative analysis methods,⁷⁴⁻⁷⁶ which consists of a two-stage coding process: level 1 structural coding and level 2 thematic coding. All analyses will be conducting by the DFCI Core. Structural coding will follow the structure of the focus group/interview guide, in which every question receives a code that is applied to the appropriate text. Thematic coding will be based on themes that arise from the structural coding and will be applied in a second pass analysis. Thematic coding allows for a grounded theoretical approach to analysis. These methods will be enhanced by ethnographic data management software (N’Vivo). This state-of-the-art program uses an organizer indexing system for coding, categorizing, searching, retrieving, and attaching analytical memos, creating a conceptual relationship network in textual data that has been taxonomically coded. Quotes that exemplify themes will also be extracted. Once the thematic analysis is complete, [name] will lead the preparation of the comprehensive thematic analysis report. Answers to the discrete items at the start of discussions will be tabulated.
- 8.2 Sample Size Considerations (Aim 1.1). In qualitative research, sampling is recommended until thematic saturation is reached and this typically occurs after including 30 participants or ≥ 4 focus groups with 6-8 participants per group.^{77,78} Therefore, we will recruit 30 patients and ≥ 24 clinicians (≥ 4 focus groups). We will begin with 1 DFCI oncology, 1 BWH PC, and 1 oncology virtual focus groups. However, if we do not achieve thematic saturation, we will recruit 3 more groups to reach thematic saturation. The DFCI ‘Core’ will provide the analytic expertise for the qualitative data analyses an thematic summaries.
- 8.3 Summary Aim 1.1 At the conclusion of Aim 1.1, we will summarize findings in the thematic analysis report, incorporate suggestions, and revise the recommended guidelines and communication tool to reflect the issues raised by our qualitative analysis.
- 8.4 Outcomes and Analyses for Aim 1.2. The outcomes of interest are shown in Table 2 below and have been adapted from [name] prior survey study testing a decision aid for screening mammography for older women.⁶⁶ We will focus on a primary outcome of intentions for mammography and will examine how various factors (race, health literacy, numeracy, anxiety, life expectancy) impact intentions. We use the sign rank and exact McNemar’s testing to compare the ‘pre’ vs. ‘post’ results for the continuous score for intention and proportion who indicate ‘yes’, respectively. To account for clustering by clinician, we will utilize random effects models if parametric assumptions hold, or alternatively using bootstrap resampling techniques to compute 95% confidence intervals for the change in intention. We anticipate a low number of missed surveys because of the CRC follow-up planned by phone, mail, or email if necessary. If a patient is missed for her ‘pre’ test survey, we will replace her to ensure enrollment of 45 with ‘pre’ and ‘post’ surveys. We will compare characteristics of those with missing surveys and missing questions to those with complete surveys to assess for any notable differences.

Table 2. Outcomes of Interest for Aim 1.2	
Outcome(s) of Interest	Outcome definitions, planned analyses

PROTOCOL TITLE:

Primary Outcomes: Patients: Frequency of change in intentions for mammography in the next year	15 point validated scale to assess ‘pre’ vs ‘post’ survey responses where scores 1-5 = yes to having mammography, 6-10 = unsure, 11-15 = no for mammography. We will use a continuous outcome of 1-15. ^{66,79}
Patients & Clinicians: Acceptability & Feasibility	Length, clarity; tabulate responses ⁸⁰ ; 75% report the tool is useful
Secondary Outcomes:	
Clinicians: satisfaction, time added/removed	Tabulate responses, prepare descriptive analyses
Patients: preferred decision-making role	‘Pre’ survey: Examine preferences for active, shared, passive decision-making ⁸¹
Patients: Decisional conflict	‘Pre’ vs. ‘Post’ survey: 16 item scale, Calculate total and sub-scale responses. Scores range 1-100, lower scores indicating higher quality decision-making ^{82,83}
Patients: Knowledge about mammography	Number of correct (10) knowledge questions on ‘pre’ vs. ‘post’ surveys. ^{66,84,85}
Patients: intentions vs. actual decisions for mammography	‘Post’: Examine whether patient intentions for mammography agree with whether mammography is scheduled or not (using chart abstraction)
Patients & Clinicians: Agreement in intentions	‘Post’ for patients and providers: degree of agreement on scores 1-15
Patients & Clinicians: life expectancy wishes	‘post’ for patients and providers: tabulate responses for willingness to discuss

8.5 Primary Outcomes for Aim 1.2: We will focus on the primary outcomes of intentions for mammography and acceptability/ feasibility. We use the sign rank and exact McNemar’s testing to compare the ‘pre’ vs. ‘post’ results for the score for intention and proportion who indicate ‘yes’, respectively. To account for clustering by clinician, we will utilize random effects models if parametric assumptions hold, or alternatively using bootstrap resampling techniques to compute 95% confidence intervals for the change in intention. We anticipate a low number of missed surveys because of the CRC follow-up planned by phone if necessary. If a patient is missed for her ‘pre’ test survey, we will replace her to ensure enrollment of 45 with ‘pre’ and ‘post’ surveys. We will compare characteristics of those with missing surveys and missing questions to those with complete surveys to assess for any notable differences. For feasibility, we will declare the tool feasible if $\geq 75\%$ of patients and physicians report usefulness of the tool.

At the conclusion of this arm, we will have preliminary data on how the communication tool impacted care, its feasibility, and about multiple exploratory, secondary endpoints. If we have difficulties with recruitment of patients or clinicians for this project, we will contact additional clinicians and patients to reach our desired accrual goals. Given the high volume of breast cancer patients and clinicians in our system, we anticipate that accrual will occur with ease.

